## **6.8.2 Analysis of the primary and key secondary endpoints**

### **6.8.2.1 Primary analysis**

The primary analysis will be performed on the ITT population.

For both primary and key secondary endpoint the number and percentage of subjects achieving the endpoint will be provided based on the subjects with observed endpoint or with intercurrent events (imputed as non-responders), i.e. excluding the subjects who are “missing at random”.

The comparisons between each active group and the placebo group will be performed pairwise. Each comparison will be done using Cochran-Mantel-Haenszel (CMH) test stratified by gender and prior biologic therapy (Yes/No). If all strata have no subjects in one of the treatment groups, a value of 0.1 will be added to all cells in the corresponding table in order to prevent dividing by 0, as suggested in Greenland and Robins (1985). The Breslow-Day test with Tarone’s adjustment for homogeneity of strata will also be performed.

This analysis will be performed on each multiple-imputed set of records and then the results will be pooled as described below.

The estimates of Mantel-Haenszel common risk (response rate) difference between each active dose group and placebo, along with 95% confidence interval, will be pooled assuming the difference is approximately normally distributed, using Rubin’s rule as described in Ratitch, Lipkovich and O’Kelley (2013).

The CMH test statistics as well as the Breslow-Day test statistic will be pooled using the Wilson-Hilferty transformation method from Ratitch, Lipkovich and O’Kelley (2013) and the pooled p-value will be provided.

If the pooled p-value of the Breslow-Day test is  $\geq 0.05$ , the treatment-by-strata interaction is not significant. In the case of heterogeneity between the strata, in-depth analysis will be conducted to understand the source of the interaction; CMH test without stratification will be used then instead of the stratified CMH test.

See sections 11.4.3, 11.4.4, 11.4.5 and 11.4.6 for sample SAS code.

Tests for superiority over placebo for the primary and the key secondary endpoint will be following the step-down approach as described in section 6.1.2.

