- Proportion of subjects with IGA score of “clear” or “almost clear” with at least two-grade reduction from baseline to Weeks 12, 20, 28, and 52
- Time to achieve PASI75 response
- Time to achieve IGA response of “clear” or “almost clear” with at least two-grade reduction from baseline
- Change from baseline in BSA involvement at Weeks 12, 16, 20, 28, and 52
- Change from baseline in PGIS at Weeks 16, 20, 28, and 52
- Proportion of subjects with improvement in PGIC at Weeks 16, 20, 28, and 52
- PASI50 and PASI75 response rate at Week 4
- [REDACTED]
- [REDACTED]
- [REDACTED]
- Steady state C_{trough} concentrations of SCD-044 at the dose levels evaluated in the study population
- Frequency, type, and severity of adverse events (AEs)

Tertiary

- Proportion of subjects with Scalp IGA “clear” or “almost clear” with at least two-grade reduction from baseline at Weeks 16, 20, 28, and 52 among subjects with a baseline Scalp IGA score of ≥ 3
- Proportion of subjects with nail psoriasis (baseline mNAPSI score of ≥ 20) who achieve at least a 75% improvement from baseline in total fingernail mNAPSI at Weeks 16, 20, 28, and 52
- Proportion of psoriatic arthritis subjects who achieve ACR20 response at Weeks 16, 20, 28, and 52.
- Proportion of subjects with PPPGA score of 0 or 1 at Weeks 16, 20, 28, and 52 among subjects with a baseline PPPGA score of ≥ 3 .

Exploratory

- Relationship between SCD-044 plasma concentrations and PASI response
- [REDACTED]
- Relationship between SCD-044 plasma concentrations and change in lymphocyte counts
- Proportion of subjects achieving ≥ 4 -point improvement in NRS from baseline at Weeks 16, 20, 28, and 52 among subjects with a baseline Itch NRS of ≥ 4

- Proportion of subjects achieving ≥ 4 -point improvement in Scalp Itch NRS from baseline at Weeks 16, 20, 28 and 52 among subjects with a baseline Scalp Itch NRS of ≥ 4
- Change from baseline in subject global assessment of PtA-P at Weeks 16, 20, 28, and 52 among subjects with PsA at baseline
- Level of lymphocyte sub-types and cytokines in blood/plasma/serum.

Other exploratory analyses may be performed based on available data. The Intent-to-Treat Population (ITT) will be used for all efficacy analyses.

Statistical Methods:

The primary and key secondary efficacy variables will be analysed using a Cochran-Mantel-Haenszel (CMH) test, stratified by gender and prior biologic therapy (Yes/No), and using the Intent-to-Treat (ITT) Population.

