8.4.1 Randomization

The subject numbers at the site will be assigned by an Interactive Response Technology (IRT) using global data across all sites and identification numbers available at a site. IRT randomization will be stratified by gender and prior biologic therapy for psoriasis. In Part II the study treatment may be reassigned according to the randomization scheme and based on the subject's PASI score at Week 16 (visit 10) [REDACTED]).

[REDACTED]

[REDACTED]

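### SAP 6.8.2.1 drops the strata from the deciding CMH test when they look heterogeneous; the stratified test should decide whatever the Breslow-Day result (small numerical effect)

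*SAP*

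**What the plan says.** Protocol Section 8.4.1: "IRT randomization will be stratified by gender and prior biologic therapy for psoriasis". The Protocol synopsis says: "The primary and key secondary efficacy variables will be analysed using a Cochran-Mantel-Haenszel (CMH) test, stratified by gender and prior biologic therapy (Yes/No"). Protocol Section 9.8 repeats this for the ITT population and leaves further detail to the SAP. No homogeneity condition appears in the readable text of either place.

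SAP Section 6.8.2.1 uses the same stratified test, and "The comparisons between each active group and the placebo group will be performed pairwise". It adds a Breslow-Day test with Tarone's adjustment, pooled over imputations. If its pooled p-value is 0.05 or more, "the treatment-by-strata interaction is not significant". If there is heterogeneity, "in-depth analysis will be conducted to understand the source of the interaction", and then "CMH test without stratification will be used then instead of the stratified CMH test". A trigger of p < 0.05 is implied; only the other side is written.

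These p-values feed the confirmatory sequence: "Tests for superiority over placebo for the primary and the key secondary endpoint will be following the step-down approach as described in section 6.1.2". Zero denominators have their own rule: "a value of 0.1 will be added to all cells in the corresponding table in order to prevent dividing by 0".

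Three other places bear on the point:

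- The tipping-point analysis in SAP Section 6.8.2.2 reuses the 6.8.2.1 test.
- In SAP Section 6.8.2.4 (subgroups) an unstratified CMH is also a fallback, but sparse data trigger it, not the Breslow-Day result.
- SAP Section 8 declares two changes from the Protocol (intercurrent-event handling and a DLQI endpoint) and says there are no others.

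**The concern.** The deciding test for the two confirmatory endpoints is chosen by a preliminary test on the outcome data. Comparisons are pairwise, so on the natural reading each dose and endpoint could end on a different test, although the SAP does not say so outright. The step-down sequence could then combine stratified and unstratified p-values.

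The response also does not fit the problem. If the effect differs between men and women, or by biologic history, pooling the strata only hides the difference. Nor does the SAP say whether the Mantel-Haenszel risk difference and its interval become unstratified too, so the p-value and the interval could come from different analyses. In the tipping-point grid, an apparent tip could reflect a change of test rather than the missing data.

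At stake are a fixed deciding analysis that matches the randomisation and the Protocol, and a little power.

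**Working it through.** **1. Inputs.** About 240 subjects randomised 1:1:1:1 (Protocol Section 4.1) gives 240/4 = 60 per arm. Tests are two-sided at 0.05 (SAP Section 6.1). Gender by prior biologic therapy gives four strata. The cap on prior biologic use is redacted. Assuming 30% and equal genders, the strata per arm are 60 × 0.5 × 0.7 = 21 and 60 × 0.5 × 0.3 = 9, that is 21/9/21/9. The response rates and power behind the sample size are not readable, so 240 cannot be reproduced, and every rate below is an assumption.

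**2. Validity of the stratified test.** In stratum h let there be n1 active and n0 placebo subjects, N in total, m responders overall and a responders on active. Then E = n1·m/N and V = n1·n0·m·(N − m)/[N²(N − 1)], and CMH = (Σ(a − E))²/ΣV on 1 df. If treatment has no effect in any stratum, all odds ratios equal 1 and this reference distribution holds. Heterogeneity exists only away from that null. In a null trial a significant Breslow-Day result is therefore chance, and under an alternative it does not invalidate the test.

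**3. Odds ratios against risk differences.** Breslow-Day tests equal odds ratios, while the SAP's summary measure (Section 2.2) is a difference in proportions. Take a constant difference of 20 points over placebo rates of 5% and 20%. The odds ratios are (0.25/0.75)/(0.05/0.95) = 6.3 and (0.40/0.60)/(0.20/0.80) = 2.7. A uniform effect on the plan's own scale can thus trigger the switch.

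**4. How often a switch occurs.** Three doses and two endpoints give six Breslow-Day tests. With no true heterogeneity, the chance of at least one switch is up to 1 − 0.95⁶ = 26% if the tests are independent; correlation lowers it.

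**5. One comparison, complete data.** With 100,000 trials per scenario and 20%, 30% or 40% prior biologic use:

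- Type I error was 4.8–5.1% under both rules, differing by at most 0.07 points.
- Used alone with strongly prognostic strata, the unstratified test was conservative (3.3–3.9% against 4.9–5.0%) and lost 3–5 points of power. The switch is rare there, so the SAP rule lost only 0.1–0.2 points.
- With effects in opposite directions between strata, the switch triggered in 70–83% of trials and changed at most 0.8% of verdicts (0.33–0.62% lost, 0.14–0.19% gained).

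With strata 21/9/21/9, 200,000 trials and a risk difference of 0 against 40 points by gender, the switch triggered in 44.3% of trials. Power fell from 86.60% to 85.72%, with no gains. A separate 100,000-trial run gave 43.9%, and 86.5% against 85.6%. Under a constant risk difference at most 0.23% of verdicts changed (0.22% in the separate run).

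**6. One comparison, multiple imputation.** This used 40,000 trials per scenario, 50 imputations, and CMH and Breslow-Day statistics pooled by Wilson-Hilferty. With 10% missing and correlation 0.8 to an earlier visit:

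| Scenario (RD in points) | Switch triggered | Rejection rate, stratified / SAP rule | Verdict changed |
|---|---|---|---|
| Null, 8% | 2.4% | 3.74 / 3.74% | 0.00% |
| Null, 5%/20% by gender | 2.6% | 3.74 / 3.71% | 0.03% |
| RD 25, placebo 8% | 3.0% | 93.91 / 93.91% | 0.01% |
| RD 20, placebo 5%/20% | 4.2% | 75.89 / 75.86% | 0.04% |
| RD 25, placebo 2%/30% | 6.5% | 90.06 / 89.91% | 0.15% |
| RD 10 vs 40 by gender | 16.6% | 94.76 / 94.71% | 0.06% |
| RD 0 vs 40 by gender | 39.5% | 85.27 / 84.74% | 0.54% |
| RD 35 vs 0 by prior biologic | 32.0% | 94.09 / 94.02% | 0.09% |

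Over all missing-data settings (5–20%), type I error was 2.3–4.4% under both rules, with a difference of at most 0.03 points. The shortfall from 5% comes from the pooling, not the switch. Verdicts changed in at most 0.18% of trials with a constant risk difference and in 0.04–0.56% with same-direction heterogeneity. The largest power loss was 0.55 points. Significance was gained in at most 0.02% of trials.

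**7. Six comparisons, complete data.** This used 60,000 trials with a shared placebo arm. At least one of the six nominal verdicts changed in 0.10–0.94% of trials under the null or a constant risk difference. With 0 against 20/30/40 points by gender it was 3.4–3.6% (balanced strata: 3.38% lost, 0.01% gained).

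**The case against.** The strongest reply is that nothing material follows. The rule is written in advance, error rates are essentially unchanged, and what changes is almost entirely lost significance, so the step-down claim is not endangered in a Phase IIb dose-ranging study. This stands, and it is why the point is minor. It does not make the switch worth keeping.

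The Protocol delegates detail to the SAP, and text near the relevant passages is redacted, so a homogeneity condition may exist out of sight. The claim of conflict therefore reaches only the readable text. A hidden condition would not make the unstratified test a better choice.

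The p < 0.05 trigger and switching by dose and endpoint are inferred; the finding that tests may be mixed depends on that reading. Writing the trigger out would close the drafting gap but keep the weaker rule.

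A sparse-data defence is not what the SAP states. The 0.1-per-cell rule is worded narrowly and would hardly cover ordinary sparse strata, so it is weak evidence. The subgroup section is better evidence: there the SAP names sparse data as its reason.

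The 3.4–3.6% counts nominal verdicts under a strong gender interaction that no passage supports, and a step-down order would gate some of those tests. The imputation model was also simpler than SAP Section 6.8.1: one earlier visit, and no logistic imputation of IGA. These are limits on the size, not on the direction.

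**Conclusion.** The concern holds and is minor. The SAP replaces the Protocol's deciding test with one that ignores the randomisation strata, on an incompletely stated data-dependent trigger, and does not declare it in Section 8. The stratified test needs no such rescue, and the planned in-depth and subgroup analyses already address heterogeneity.

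The effect on type I error is negligible. The power cost for a single comparison runs from nil to about 0.9 points, with practically no offsetting gain when effects share a direction. These sizes rest on assumed response rates, missingness and share with prior biologic therapy. The step-down order is redacted, so the effect on the sequence itself was not computed.

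**What to change.** Delete the switch from SAP Section 6.8.2.1. State instead that the stratified CMH test and the stratified Mantel-Haenszel risk difference are the deciding analysis regardless of the Breslow-Day result, there and wherever that test is reused, including Section 6.8.2.2.

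Report the Breslow-Day test and the four stratum-specific risk differences with 95% confidence intervals descriptively, next to the 6.8.2.4 subgroup analyses. With about 9 to 21 subjects per arm in each stratum (assumed), those intervals will be wide and should be read accordingly. Show the unstratified CMH as a sensitivity analysis at most. If the sponsor keeps the switch, it should at least define the trigger, say which estimate and interval go with it, and list it in Section 8.

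The cost is one or two sentences, with no extra data or subjects and no change in sample size.

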### **6.8.2.2 Sensitivity analyses**

The following sensitivity analyses will be performed to explore the effects of missing data on the primary endpoint and key secondary endpoint:

1. Analysis similar to the primary analysis on the ITT population, but without multiple imputations with “missing at random” endpoint values and values after intercurrent events imputed using Last Observation Carried Forward (LOCF) approach. For this analysis the latest available post-baseline assessment of PASI or IGA will be carried

forward to impute missing Week 16 assessments. Subjects with missing baseline or no post-baseline assessment prior to Week 16 will be excluded from this analysis.

Additionally for subjects with intercurrent events the last available post-baseline assessment obtained prior to the start of the intercurrent event will be used to impute Week 16 assessment. If no such assessment is available, the subject will be excluded from analysis.

2. Analysis similar to the primary analysis on the ITT population, but without multiple imputations with “missing at random” endpoint values and values after intercurrent events imputed using Active Treatment Worst Case (ATWC) approach. For this analysis any subjects in the Placebo group with missing response or with an intercurrent event will be imputed as responders, while any subjects in any active treatment group with missing response or with an intercurrent event will be imputed as non-responders.
3. Tipping point analysis. This analysis will consist of a series of analyses similar to the primary analysis of the primary and key secondary endpoints with varying proportions of subjects who are “missing at random” imputed as responders or non-responders. The analysis will be performed for each active treatment group vs. placebo and for each combination of X1, the percentage of subjects “missing at random” in the placebo group and X2, the percentage of subjects “missing at random” in the active group. Both X1 and X2 will range from 0% to 100% in steps of 20%.

For each pair of (X1, X2), X1% of subjects will be randomly drawn from the subjects “missing at random” in placebo group and X2% of subjects will be randomly drawn from the subjects “missing at random” in the active group. These randomly selected X1% subjects in the placebo and X2% subjects in the active group will be imputed as responders. The remaining subjects “missing at random” will be imputed as non-responders. Analysis then will be conducted using the combined observed data and imputed data for each treatment group using the CMH test as described for the primary analysis in section 6.8.2.1. The random draw procedure will be repeated 49 times for each pair of (X1, X2) and the median p-value for the active vs. placebo comparison will be used for the conclusion. The estimate of the CMH common risk (response rate) difference between the treatment groups associated with the p-value selected as median will also be shown. If the same median p-value is obtained in more than one of the 49 random draws, the largest difference will be selected. The random seed for the draw will be preset as 441914 to ensure the analysis is repeatable and amenable to validation via double programming. If one pair of X1 and X2 is found to reverse the study conclusion (i.e., median p-value  $> 0.05$  [tipping point analysis will be performed only if the primary analysis reached p-value  $\leq 0.05$ ]), then these parameters will be the tipping points.

### 6.8.2.3 Supplementary analyses

The following supplementary analyses will be performed:

1. Analysis similar to the primary analysis, but on the Per Protocol population using observed cases only with no imputations.
2. The primary and key secondary endpoint will be analyzed using generalized linear mixed model for repeated measures with fixed effects for treatment, visit (time

variable), treatment by visit interaction, gender and prior biologic therapy (yes/no). Visits 7, 8, 9 and 10 will be used. Visit is random effect within Subject with covariance structure. The model will be used to estimate the probability of response (expressed as percentage) at each visit with its 95% confidence interval. Odds ratio for response at Visit 10 (Week 16) for each active treatment vs. placebo with its 95% confidence interval will also be presented with the p-value for the hypothesis of no difference. See section 11.4.7 for details and sample SAS code.

#### **6.8.2.4 Subgroup analyses**

The primary analysis of the primary and key secondary endpoints will also be repeated by subgroups:

[REDACTED]

In the subgroup analysis by gender and prior biologic therapy the subgroup factor will not be used as stratification factor in the CMH test.

The Breslow-Day test will be performed for each subgrouping variables in order to verify the homogeneity of endpoints. In the case of sparse data non-stratified CMH test will be used instead of the stratified CMH.

#### **6.8.3 Analysis of other endpoints**

All other endpoints will be summarized using the ITT population.

3. mNAPSI. The scale consists of 7 assessments for each fingernail. The total score is the sum of items scores for all assessments and all fingernails. It can range from 0 to 130 (maximum of 13 for each fingernail), with higher mNAPSI scores denoting more severe disease activity.

#### **6.8.3.2 Binary endpoints**

Binary endpoints include:

- PASI50, PASI75, PASI90, PASI100 responses (i.e. reduction of at least 50%, 75%, 90% and 100% from baseline in PASI)
- IGA response (achieving IGA score of “clear” or “almost clear” with at least two-grade reduction from baseline)
- achieving PGIC improvement,
- Scalp IGA response (achieving Scalp IGA score of “clear” or “almost clear” with at least two-grade reduction from baseline).
- mNAPSI response (achieving at least a 75% improvement from baseline in total fingernail mNAPSI)
- ACR20 response (see the definition in the next section)
- achieving PPPGA score of 0 or 1
- achieving DLQI scores of 0 or 1
- achieving  $\geq$  4-point improvement in Itch NRS from baseline
- achieving  $\geq$  4-point improvement in Scalp Itch NRS from baseline.

Note that for all binary endpoints above that involve change from baseline or percent change from baseline, Part II baseline will be used for the groups that switch treatment in Part II, while Part I baseline will be used for the groups that stay on the same treatment throughout the study.

Number and percentage of subjects achieving these endpoints will be presented by treatment group along with 95% confidence interval for percentages based on binomial proportion.

Additionally shift tables will be created for IGA presenting shifts from baseline to post-baseline visits in Part I and Part II separately.

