#### 4.4 Tertiary endpoints

Tertiary endpoints of this study are:

- Proportion of subjects with Scalp IGA “clear” or “almost clear” with at least two-grade reduction from baseline at Weeks [REDACTED] and 52 among subjects with a baseline Scalp IGA score of  $\geq 3$
- Proportion of subjects with nail psoriasis (baseline mNAPSI score of  $\geq 20$ ) who achieve at least a 75% improvement from baseline in total fingernail mNAPSI at Weeks [REDACTED] and 52
- Proportion of psoriatic arthritis subjects who achieve ACR20 response at Weeks [REDACTED] and 52
- Proportion of subjects with PPPGA score of 0 or 1 at Weeks [REDACTED] and 52 among subjects with a baseline PPPGA score of  $\geq 3$

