#### 4.5 Exploratory endpoints

Exploratory endpoints include:

- [REDACTED]
- [REDACTED]
- [REDACTED]
- Proportion of subjects achieving  $\geq$  4-point improvement in Itch Numeric Rating Scale (NRS) from baseline at Weeks [REDACTED], and 52 among subjects with a baseline Itch NRS of  $\geq$  4
- Proportion of subjects achieving  $\geq$  4-point improvement in Scalp Itch NRS from baseline at Weeks [REDACTED] and 52 among subjects with a baseline Scalp Itch NRS of  $\geq$  4
- Change from baseline in subject global assessment of PtA-P at Weeks [REDACTED] and 52 among subjects with PsA at baseline
- [REDACTED]

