- Part II Baseline is defined as the last assessment, scheduled or not, prior to the first dose of the study drug in Part II. Part II baseline will be used in analysis of findings collected in Parts II, III and IV for subjects who were re-randomized in Part II to another treatment (i.e. SCD-044 [ ] or [ ] after being treated with Placebo in Part I or to SCD-044 [ ] after being treated with SCD-044 [ ] or [ ] in Part I). Throughout this SAP, if the word “baseline” is used without qualification “Part I” or “Part II”, it will refer to Part I baseline.

In by-visit summaries, only data collected on scheduled visits/timepoints will be summarized. Data from unscheduled assessments will be included in listings and may be used in determination of baseline if applicable.

Relative days will be calculated relative to date of first dose of the study drug. Relative days will be calculated as follows only when the full assessment date is known (i.e., partial dates will have missing relative days).

For assessment on or after the day of first dose of the study drug:

Relative Day = Date of Assessment – Date of First Dose of Study Drug+1.

For assessment before the day of first dose of the study drug:

Relative Day = Date of Assessment – Date of First Dose of Study Drug.

All dates will be displayed in DDMMYY format.

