### **6.8.3.5 Time to PASI75 and IGA responses**

Time to achieve PASI75 and time to achieve IGA response will be summarized separately for the Part I of the study, for the Parts II and III of the study for subjects re-randomized at Week 16 and for the study overall for subjects receiving the same treatment throughout the study.

In the analysis of Part I subjects will be analyzed by treatment groups based on the treatment that the subject received in Part I (see [Section 6.1.1](#)). Time to achieve PASI75 will be defined as the number of weeks from the day of the first dose of the study drug to the first PASI75 assessment in Part I (i.e., up to and including Week 16 visit) when PASI75 is achieved. For subjects who never achieve PASI75 in Part I the time will be censored at the last PASI75 assessment in Part I.

Similarly, time to achieve IGA response in Part I will be defined as the number of weeks from the day of the first dose of the study drug to the first IGA assessment in Part I (i.e., up to and including Week 16 visit) when IGA score of 'clear' or 'almost clear' with at least two-grade reduction from Baseline is achieved. For subjects who never achieve IGA response in Part I the time will be censored at the last IGA assessment in Part I.

The analysis of the Parts II and III will be conducted within subjects who were re-randomized at the start of Part II. In this analysis, subjects will be analyzed by treatment groups based on their treatments in Part II (see [Section 6.1.1](#)). Times will be defined similarly to the analysis of Part I, except they will start at the time of the switch to a new treatment in Part II and will be

censored at the last assessment in the study. Part II baseline will be used when determining PASI and IGA responses.

The analysis for the study overall will be conducted only for subjects who were initially randomized to any dose of SCD-044 and did not switch treatments during the study. In this analysis subjects will be analyzed by treatment groups based on their treatments in Part I. Times will be defined similarly to the analysis of Part I, except then will be censored at the last assessment in the study.

Quartiles of time to achieve PASI75 and time to achieve IGA response (based on the Kaplan-Meier method) with their 95% confidence intervals (using Brookmeyer and Crowley method with log-log transformation) will be calculated by treatment group.

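### For groups that switch in Part II, IGA response is a two-grade drop from Week 16, so subjects already clear or almost clear cannot respond and count as failures

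*SAP*

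**What the plan says.** SAP 6.8.3.2 defines the first rule as "IGA response (achieving IGA score of “clear” or “almost clear” with at least two-grade reduction from baseline", and the scalp rule as "Scalp IGA response (achieving Scalp IGA score of “clear” or “almost clear” with at least two-grade reduction from baseline". Itch and scalp itch response are drops of at least 4 points. The section then adds a note: "for all binary endpoints above that involve change from baseline or percent change from baseline, Part II baseline will be used for the groups" (meaning those whose treatment changes in Part II). Groups that keep one treatment are scored from Part I baseline.

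SAP 6.1 supplies the reference point: "Part II Baseline is defined as the last assessment, scheduled or not, prior to the first dose of the study drug in Part II". In practice this is Visit 10 (Week 16), where IGA, Scalp IGA and itch are all scored. For time to response in Parts II and III, SAP 6.8.3.5 says "Part II baseline will be used when determining PASI and IGA responses". The clock starts at the switch, and subjects without an event are censored at their last assessment.

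Two endpoint families carry an entry floor. SAP 4.4 counts scalp response "among subjects with a baseline Scalp IGA score of" at least 3, and SAP 4.5 counts itch response "among subjects with a baseline Itch NRS of" at least 4 (scalp itch likewise). Neither names a Part. SAP 6.1 says that where the word baseline carries no Part label, "it will refer to Part I baseline". IGA has no floor beyond trial entry, which requires IGA of 3 or more (Protocol 4.2).

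Protocol 9.8 defines the IGA endpoint at Weeks 20, 28 and 52 as a reduction from baseline, and the protocol's Baseline Visit is Week 0. SAP section 8 does not list re-baselining among the changes from the protocol.

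**The concern.** A rule that combines an absolute grade with a fixed drop works only if everyone starts high enough to fall that far. Entry at IGA 3 or 4 guarantees this in Part I. Nothing guarantees it at Week 16.

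The subjects most likely to be caught are placebo subjects who improved. SAP 6.1.1 lists two Placebo/SCD-044 groups under Part I Responders (at least PASI50), so those columns are selected for low Week 16 scores. The never-switched columns are scored from Week 0. Two subjects with the same scores at every visit can thus be classified differently only because one changed treatment. At stake are the post-Week 16 IGA response rates, which are secondary endpoints, the time-to-IGA-response quartiles, and the scalp (tertiary) and itch (exploratory) rates.

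The point is confined to absolute-drop rules. DLQI 0/1 and PPPGA 0/1 involve no change. PASI and mNAPSI response are percentage rules, which remain attainable from any score above zero.

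**Working it through.** The plan states no figure for this point, so there is nothing to reproduce. The check enumerates the rules and then bounds the effect.

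**Step 1: enumeration.** Let b be the Part II baseline score and y a later score. IGA or Scalp IGA response means y ≤ 1 and b − y ≥ 2. Itch response means b − y ≥ 4.

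| b (IGA or Scalp IGA) | later scores that respond |
|---|---|
| 0 | none |
| 1 | none |
| 2 | 0 only |
| 3 or 4 | 0 or 1 |

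| b (itch NRS) | later scores that respond |
|---|---|
| 0 to 3 | none |
| 4 | 0 only |
| 5 to 10 | 0 up to b − 4 |

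**Step 2: compare with Part I baseline.** From a Part I IGA of 3 or 4, any later grade of 0 or 1 meets the two-grade drop (3 − 1 = 2). Five (Week 16, later) pairs are therefore responses from Part I baseline and non-responses from Part II baseline: (0,0), (0,1), (1,0), (1,1) and (2,1). For example, a subject with IGA 3 at Week 0, 1 at Week 16 and 0 at Week 28 is a responder in a never-switched group (3 − 0 = 3) and a non-responder in a switch group (1 − 0 = 1).

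**Step 3: the floors.** Take itch 8 at Week 0, 3 at Week 16 and 0 at Week 28. With a Part I floor the subject is in the denominator (8 ≥ 4) and fails (3 − 0 = 3 < 4) although free of itch. With a Part II floor the subject leaves the denominator (3 < 4). If floor and drop share a baseline, every included subject can meet the rule, since a scalp score of 3 or more can fall to 1 or below by two grades and an itch score of 4 or more can fall by 4.

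**Step 4: size for IGA.** Let s be the share of a switch column at IGA 0/1 at Week 16 (not in the documents; assumed 5% to 30%), r the response rate among the others, and m the share of the low subjects still at 0/1 later.

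- Ceiling under the SAP rule: 1 − s
- Reported rate, SAP rule: (1 − s)r
- Reported rate, Part I baseline: (1 − s)r + s·m
- Reported rate, Part II baseline limited to subjects at IGA 2 or more: r

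With r = 50% and m = 100%, chosen only for illustration:

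| s | ceiling | SAP rule | Part I baseline | Part II, limited |
|---|---|---|---|---|
| 5% | 95% | 0.95 × 50 = 47.5% | 47.5 + 5 = 52.5% | 50% |
| 10% | 90% | 0.90 × 50 = 45% | 45 + 10 = 55% | 50% |
| 20% | 80% | 0.80 × 50 = 40% | 40 + 20 = 60% | 50% |
| 30% | 70% | 0.70 × 50 = 35% | 35 + 30 = 65% | 50% |

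The gap between the second and third rules is s·m. Subjects going from IGA 2 to 1 would widen it; the table leaves them out.

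**Step 5: time to response.** A barred subject never has an event. If a share s is barred and followed to the end, and no one else is censored, the Kaplan-Meier response curve cannot pass 1 − s. At s = 30% it stops at 70%, so the third quartile that SAP 6.8.3.5 asks for is never reached.

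**Step 6: column size.** 240 subjects in four equal arms gives about 60 on placebo. If 10% to 30% reach PASI50 (assumed), that is 6 to 18 subjects, or 3 to 9 in each of two equal columns before dropout. One barred subject then takes between 1/9 (11 points) and 1/3 (33 points) off the attainable rate.

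**The case against.** Re-baselining is deliberate and is applied consistently in SAP 6.1, 6.8.3.1, 6.8.3.2, 6.8.3.3 and 6.8.3.5: it asks what changed after the new treatment began. For a move from IGA 2 to 1 that is a fair choice of estimand. It does not justify keeping in the denominator subjects for whom the answer is fixed in advance.

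The sentence in SAP 6.1 just before the default says that Part II baseline applies to findings from Parts II to IV in re-randomized subjects who change treatment. Read broadly, that could move the scalp and itch floors to Part II, and low subjects would then drop out instead of failing. This stands as an ambiguity. It does not help IGA, which has no floor to move.

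SAP 6.8.3.4 tabulates every IGA and Scalp IGA grade, and 6.8.3.2 adds IGA shift tables, so clear subjects remain visible there. That stands too, but itch NRS is not among those categorical endpoints, and the time-to-response analysis has no such companion.

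Scoring from Part I baseline credits SCD-044 with improvement gained on placebo. This is a real cost. With a clock starting at the switch it would record an immediate event that belongs to the placebo period, so Part I baseline should not simply be carried into 6.8.3.5. The PASI50 grouping in 6.1.1 does not show Week 16 IGA status either, so that has to be added.

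A reader might infer that the tables will make late-treated subjects look far worse, or that their rates will fall to near zero. The documents do not support this: they give no Week 16 distribution, and the table shells with their headers and footnotes are a separate document. A reader might also infer that the trial's main result is affected. It is not: the primary and key secondary endpoints are assessed at Week 16 from Part I baseline.

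**Conclusion.** The concern holds. For IGA it follows from the wording alone: a switcher at grade 0 or 1 at Week 16 is a non-responder at every later visit and can never be an event in the Part II/III time analysis, even if clear to Week 52. For Scalp IGA, itch NRS and scalp itch NRS it holds under the SAP's own default for the floors, and the text needs to settle the other reading.

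The only assumption-free measure of size is the ceiling of 100% minus the share low at Week 16. That share, and every percentage built on it above, is assumed. The columns most exposed are probably small.

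The consequence is limited to descriptive results after Week 16. No between-group test is specified for them, and SAP 6.1.2 rules out inference from p-values on other endpoints. The text should still be corrected, because the rule counts sustained clearance as failure, differs from the protocol's endpoint, and is not declared as a change.

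**What to change.** 1. **SAP 6.8.3.2, IGA and Scalp IGA.** For switchers, define response as grade 0/1 with the two-grade drop taken from Part I baseline, as in the protocol endpoint. Show Week 16 IGA response status alongside, so that gains made before the switch are visible. A Part II-baseline IGA rate may be kept as an addition if its denominator is limited to subjects whose Part II baseline allows the drop (IGA 2 or more).
2. **Itch and scalp itch NRS.** Take the floor and the 4-point drop from the same baseline. If the drop runs from Part II, require a Part II score of at least 4.
3. **SAP 6.8.3.5.** Do not pair a Part I-baseline event with a clock that starts at the switch. Limit the Part II/III time-to-IGA-response analysis to switchers not already in IGA response at Week 16 whose Part II baseline allows the event, and report maintenance of response separately for the others.
4. **Labelling.** State the baseline used in each column, and list the re-baselining in SAP section 8.

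The cost is SAP wording and a few more programmed columns; all the data are already collected. The drawback is that the Part I-baseline rates include improvement gained before the switch, which the Week 16 status display makes visible but does not remove.
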